## COVER PAGE

Study Title	Interventions To Help Asthma Clinical Adherence (ITHACA)
NCT Number	NCT02999789
Document Description	Statistical Analysis Plan
Document Date	23 February 2021

This study was a quasi-experimental single-center pilot trial that used a staggered implementation design which measured the effect of an asthma medication reminder system device on asthma controller medication adherence during an initial run-in period and an intervention period. Because the intervention was a reminder system, it was not possible to 'blind' the participants.

For the pilot phase, we aimed to recruit children ages 5 to 17 years with a diagnosis of persistent asthma who required a daily inhaled corticosteroid metered dose inhaler and whose guardian was the person responsible for directly administering or supervising the administration of their daily asthma medication. Our target sample size at the study's onset was to recruit 30 children ages 5 to 17. The sample size was limited by the budget limitations. Based on cost-efficiency and limitations, 30 participants would give a general estimate of the effectiveness of this intervention. The study results could be used for the power calculations for a future, larger RCT. Assuming a positive effect of reminder systems and a baseline adherence rate of 60%, with 15 patients in each group, with a power of 0.80, an alpha of 0.05, there would be enough power to detect a 15% change in adherence which is within the range of improvement reported. This percentage change translated to a Number Needed to Treat (NNT) of 6 patients.

We only recruited from a University-affiliated clinic serving publicly insured children. We recruited children whose asthma subspecialist or health care provider practiced at the Children's Health Center (CHC) at Zuckerberg San Francisco General Hospital. We only recruited from the primary care clinics and the asthma clinic. We only recruited children whose guardian responsible for administering their daily asthma medication had Limited English Proficiency (LEP) and whose primary language was Spanish. Lastly, we only included children whose daily inhaled corticosteroid was a metered dose inhaler (MDI) that was either Flovent (fluticasone propionate) HFA (Hydrofluoroalkane) or Qvar (beclomethasone dipropionate) HFA. This was the case because the SmartInhaler device was only available for those two MDIs.

We excluded children whose guardian(s) had a low health literacy based on the Short-test of Functional Health Literacy in Adults in Spanish (S-SFHLLA) and those who were unable to demonstrate correct medication technique based on standard evaluation after completion of a standard teaching protocol. Patients who were using a long acting beta-agonist as part of their asthma management plan were excluded. As a result, the study focused on children who fell into the mild persistent asthma classification. We excluded patients whose guardian responsible for administering their daily asthma medication did not have a Bluetooth enabled cell phone capable of receiving text messages, did not have an available reliable power outlet where they could recharge the battery of their SmartInhaler device, did not have an operating system of iOS or Android on their cell phone, or did not have a data plan with their cellular phone plan. We excluded patients with chronic lung disease. We excluded children whose guardian (s) did not directly administer their daily asthma medication or directly supervise the children self-administering their daily asthma medication. Lastly, we excluded patients whose asthma medication regimen was being managed by an asthma subspecialist or health care provider outside of the Children's Health Center at Zuckerberg San Francisco General Hospital.

There were three recruitment strategies. We posted advertisements about the study around the hospital with a study call back number. We also contacted potential subjects who had previously consented to being contacted for participation in research from earlier asthma studies via mail. Lastly, we identified prospective subjects through a chart review of future primary care and asthma clinic visits and asked the health care provider to ask patient's guardians during the visit if they were interested in being contacted by study staff regarding ITHACA. If the patient's guardians agreed to be contacted, we would call them and do the screening form over the phone to make sure they met the inclusion and exclusion criteria. The primary mentor for this study, [name], is a Principal Investigator for one of the research sites for AsthmaNet, a nationwide clinical research network created by the National Heart Lung and Blood Institute. Aside from the principal investigator, a research assistant was hired. Their main duties would

be to lead recruitment and retention of patients, collect data, conduct follow-up visits and oversee day-to-day study tasks.

[figure not shown]
A summary of the different events at each visit is detailed in **Figure 2**. After consent was obtained from both the child and caregiver, we collected demographic data on the child (e.g., age, gender, age of asthma diagnosis, occupation, languages spoken at home, relatives with asthma, smoking exposure) and the characteristics of the patient's disease (e.g., severity, medications used, previous hospitalizations, current provider, subspecialty provider for asthma [if any], duration of use of current medications) which may affect adherence to their medication or asthma symptom control. The subject's guardian then completed a few surveys including the Pediatric Asthma Quality of Life Questionnaire (PAQLQ), the Pediatric Asthma Caregiver Quality of Life Questionnaire (PACQLQ), the Parent Asthma Management Self-efficacy (PAMSE) scale and a survey that included self-described medication taking behavior and a decision-making survey (a modified Reported Adherence to Medication (RAM) Survey). The RAM Survey, is a 3 question instrument, which helps describe and predict potential types of nonadherence behavior. The PAQLQ is an asthma-specific quality of life scale that has been validated in children and adolescents aged seven to 17 years and it has officially been translated into Spanish (Juniper, 1996). The PACQLQ is an asthma-specific quality of life scale for caregivers of children with asthma. (Juniper, 1996). The PAMSE measures parental self-efficacy for the management and prevention of acute asthma exacerbations. (Bursch, 1996) Since the RAM survey and PAMSE scale are available in English only, they were translated into Spanish using a systematic approach (Brislin, Lonner & Thorndike, 1973). The child's guardian also completed the Childhood Asthma Control Test (C-ACT). Although the C-ACT is used only for patients ages 4 to 11, we used this for children older than 11 because this version is only to be filled out by the parent or guardian. The C-ACT is a 7 item scale, with scores ranging from 0 (poor asthma control) to 27 (complete asthma control). In general, a C-ACT score >19 indicates well-controlled asthma.

The final step prior to the end of the initial visit was giving the participant and guardian the SmartInhaler device. Participants received either a Flovent or a Qvar SmartInhaler device depending on which daily controller medication they were taking. The SmartInhaler device unobtrusively would record every time the asthma daily medication is taken and communicate this information to the study center.

If the activated reminder system was activated and the participant did not take their daily medication, the SmartInhaler would send a text message to the patient's cell phone in Spanish reminding them to take their daily medication. Only the Flovent SmartInhaler featured an additional audio-visual reminder on the device that could also remind study participants to take their missed medication. Due to the Flovent SmartInhaler's additional feature reminding patients, participants were stratified into two groups according to the type of SmartInhaler they were using. The aim was to recruit 15 participants to use the Flovent SmartInhaler and 15 participants to use the Qvar SmartInhaler.

Data regarding daily asthma medication adherence was obtained using the SmartInhaler. Medication adherence for each medication would be calculated as a percentage of total number of doses received during the study period divided by the total number of doses prescribed. As a result, the percentage ranged from 0 to 100. The activated reminder system was initially deactivated but the SmartInhaler was turned on since it was going to be measure baseline adherence. A power cord given to the participants and guardians so they could recharge the battery of the SmartInhaler when it became depleted. The guardians of the participants were compensated with a \$20 gift card for their time. The ACT, RAM, PAQLQ, PACQLQ, and PAMSE were completed at every study visit.

The time interval between visit 1 and visit 2 was the run-in period. During the run-in period, we determined baseline daily asthma controller medication rates using the SmartInhaler system without the activated reminder system and we also assessed baseline asthma symptom control.

**Figure 1:** Study Design and Events for Each Visit (ACT = Asthma Control Test; RAM = Reported Adherence Medication Scale)

During visit 2, participants were randomized by a block design to ensure participants were equally distributed among both study groups. The University’s Clinical and Translational Science Institute was consulted to assist in creating the randomization through computer generated random numbers. Once those numbers were generated, they were placed in envelopes by non-study personnel. A staggered implementation design was implemented in order to offer the intervention to all participants. Half the patients were randomly selected to have the reminder system activated during this 2nd visit. The reminder system was activated and data regarding daily asthma medication adherence was obtained using the SmartInhaler and sent to the data center. The other half did not have the reminder system activated in order to provide for a concurrent control group. That group had delayed activation until the 3rd visit.

During the 3rd visit, the rest of the participants had the reminder system activated. As for the group that had the SmartInhaler reminder system activated at the 2nd visit, we collected the SmartInhaler devices and administered a modified version of the Technology Acceptance Model (TAM) questionnaire which collects patient feedback about the device’s usefulness. The TAM determines the user acceptance of any technology perceived usefulness and perceived ease of use factors. The TAM questionnaire, first developed by Davis (1993) and validated in different contexts by several researchers (Nair & Das, 2011), consisted of 17 questions, of which 13 were on a 5-point Likert-type scale questionnaire, with the scale ranging from 1 (strongly agree) to 5 (strongly disagree). A modified version of this questionnaire was used for this study. For the delayed activation group, their final visit was their 4th visit. At that final visit, we collected the SmartInhaler devices and obtain patient feedback on its usefulness by administering the TAM.

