## DATA ANALYSIS

In order to analyze the data, we consulted a statistician from the UCSF Clinical and Translational Science Institute (CTSI). The statistician analyzed the entire data set using statistical software. Demographic characteristics of each group were assessed to see if there were obvious disproportionate distributions of certain characteristics in the groups which may have affected the adherence. Medication adherence for each medication was calculated as a percentage of the total number of doses received during the study period divided by the total number of doses prescribed. As a result, this percentage ranged from 0 to 100. Medication adherence percentages and asthma symptom control scores during both the run-in and intervention periods were measured and the differences between the two time periods (Adherence Delta  $\Delta$  and asthma symptom control Delta) was calculated for each patient. For objectives 1 & 2, we compared the mean “adherence delta” and “asthma symptom control delta” for each group using a student t-test.

Finally for the third objective, in order to assess if there were specific patient behavior characteristics which were associated with the success of a novel asthma medication reminder system, we identified those patients whose adherence rates increased from baseline. We compared the scores of the RAM Scale for those patients with a change in adherence compared to those patients with no improvement in adherence. We used a chi-squared test to assess if the RAM scores which suggest 'forgetful nonadherence' were associated with improved adherence rates during exposure to the reminder system. Analyses were performed using SAS version 9.4 (SAS Institute, Cary, NC).

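### The stated 80% power for a 15% change with 15 per group does not follow from the inputs given, and neither does the NNT of 6

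*SAP*

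**What the plan says.** The sample size paragraph (SAP, Cover Page section) sets the number first: "Our target sample size at the study's onset was to recruit 30 children ages 5 to 17". It gives the reason: "The sample size was limited by the budget limitations". It presents the study as a pilot whose results could serve the power calculation of a larger RCT.

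It then makes a formal power claim. From a baseline adherence of 60% and a positive effect of reminders, "with 15 patients in each group", it states that "with a power of 0.80, an alpha of 0.05, there would be enough power to detect a 15% change in adherence". The next sentence adds: "This percentage change translated to a Number Needed to Treat (NNT) of 6 patients".

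The paragraph names no SD, no test and no sidedness, and does not say whether 15% is absolute or relative.

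The later text on visit 2 defines the randomised comparison: "Half the patients were randomly selected to have the reminder system activated", with the other half as concurrent control until visit 3. The Data Analysis section defines adherence per patient as doses received over doses prescribed: "As a result, this percentage ranged from 0 to 100". It takes each patient's difference between run-in and intervention periods and compares the mean difference "for each group using a student t-test". It does not give the sidedness of that test.

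**The concern.** A baseline rate, a change, a group size and an alpha are the inputs of a two-proportion calculation, and an NNT belongs to the same setting. With 15 per group, such a calculation cannot give 80% power for 60% against 75%. The planned endpoint, however, is a continuous change score, and for that the power cannot be computed without an SD, which is missing.

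The practical stake is how a null result is read. A stated power of 80% tells the reader that a true 15-point difference would be missed one time in five. If the real figure is nearer one in two, a non-significant result carries much less information than the SAP implies. Because the results are offered for planning a larger RCT, it also matters that no planning SD is on record to set beside the SD that the pilot observes.

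**Working it through.** **Inputs from the SAP.** n = 15 per group; alpha = 0.05; stated power 0.80; baseline 60%; change 15%. Sidedness is not given, so both are shown. The change is taken first as 15 percentage points, then as 15% relative (60 × 0.15 = 9 points).

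**1. Attempt to reproduce 80% as two proportions, 0.60 against 0.75.**

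Power = Φ{[δ√n − z·√(2p̄q̄)] / √(p₁q₁ + p₂q₂)}, with p̄ = 0.675.

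- δ√n = 0.15 × √15 = 0.581
- √(2 × 0.675 × 0.325) = 0.662
- √(0.24 + 0.1875) = 0.654
- Two-sided: (0.581 − 1.960 × 0.662)/0.654 = −1.097, so power = 13.6%
- One-sided: (0.581 − 1.645 × 0.662)/0.654 = −0.778, so power = 21.8%

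Exact enumeration gives 14.6% (Pearson chi-squared, two-sided) and 6.2% (Fisher, two-sided). A relative change, 60% to 69%, gives 7.3% two-sided and 12.8% one-sided.

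Required n for 80% = (1.960 × 0.662 + 0.842 × 0.654)² / 0.15² = 3.417/0.0225 = 151.9, so 152 per group two-sided; the same formula gives 120 one-sided. With 15 per group, the other arm would have to reach about 99.5% for 80% power two-sided. No variant tried on this reading comes near the stated figure.

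**2. The t-test of the Data Analysis section: between-group difference in mean adherence change.**

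Noncentral t, 28 degrees of freedom, noncentrality (δ/SD)·√(15/2). Solving for 80% power:

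- Two-sided: δ/SD = 1.060. For 15 points the SD must be at most 15/1.060 = 14.2; for 9 points, 9/1.060 = 8.5.
- One-sided: δ/SD = 0.931. For 15 points the SD must be at most 15/0.931 = 16.1.

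The SAP gives no SD, so the values below are assumptions. Expected 95% CI half-width = t(0.975, 28) × SD × √(2/15) = 2.048 × 0.365 × SD = 0.748 SD.

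| Assumed SD of change (points) | Power, two-sided | Power, one-sided | 95% CI half-width (points) |
|---|---|---|---|
| 10 | 98% | 99% | 7 |
| 14 | 81% | 89% | 10 |
| 15 | 75% | 85% | 11 |
| 20 | 51% | 64% | 15 |
| 25 | 35% | 48% | 19 |
| 30 | 26% | 38% | 22 |

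**3. NNT.** 1/0.15 = 6.67, which rounds up to 7 by convention. An NNT of 6 would need 1/6 = 16.7 points. If 15% is relative, 1/0.09 = 11.1. More basically, an NNT counts patients per additional responder, and the power paragraph defines no responder. The third objective does split patients into improved and not improved, but it attaches no 60% baseline rate to that split.

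**The case against.** The strongest reply is that the 14% figure belongs to an analysis the SAP does not plan. Adherence is a per-patient percentage compared by t-test, and on that test no arithmetic error has been shown: an SD of 14 gives 81% power two-sided, and an SD of 15 gives 85% one-sided. What is left is an unstated SD, which the protocol may hold. This stands in part, and it is why the claim is called unsupported, not disproved, on the planned test. It does not rescue the sentence. The SAP itself makes the power claim and lists inputs for it, those inputs together with the NNT are the binary ones, and they do not give 80%.

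Sidedness is also open. The SAP names a Student t-test without a side, and its assumption of a positive effect permits a one-sided reading. That moves the SD limit only from 14.2 to 16.1.

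A within-patient test would tolerate a larger SD: 19.3 points with 15 patients or 28.3 with 30, two-sided. The Data Analysis section compares groups, so this shows ambiguity in the claim and not support for it. Nor does it help that 15 and 15 are also the recruitment targets for the two device types; the arithmetic is the same for any two groups of 15.

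Finally, this is a budget-limited pilot, the NNT is partly a rounding matter, and no decision in the SAP depends on it. All true. That defends the choice of 30 children, which is not in dispute, but not an explicit statement of 80% power.

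**Conclusion.** The concern holds and should be fixed. As a comparison of proportions, the stated power is wrong by a wide margin: about 14% two-sided or 22% one-sided, against 80%. As the between-group t-test, it depends on an SD the SAP does not give. If the test is two-sided, the chance of missing a true 15-point difference is 25%, 49%, 65% and 74% at assumed SDs of 15, 20, 25 and 30, against the implied 20%; at an SD of 14 or less the claim would be met. The NNT of 6 is wrong numerically and does not suit the endpoint. The t-test figures assume 15 analysed per randomised arm and a common SD. Sample size, endpoint and test are unaffected.

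**What to change.** If the sponsor has the basis of the 80% figure, and it relates to the between-group comparison of adherence change, keep the sentence and add the SD of the change, its source, the test, the sidedness, and whether 15% is absolute or relative.

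Otherwise delete the power claim and put in its place wording such as:

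> The sample size of 30 is set by budget. With 15 per randomised arm, a two-sided 5% t-test has 80% power for a difference of 1.06 SD of the adherence change: 15 points only if the SD is about 14 or less, 21.2 points if it is 20, 26.5 points if it is 25. The expected 95% CI half-width is about 0.75 SD. The purpose of the pilot is to estimate the SD and the effect, with a confidence interval.

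Remove the NNT sentence either way. Because the SAP is written in the past tense, enter the change as a dated correction so that the planning record stays visible.

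The cost is wording only, plus a less favourable stated power. No extra patients are needed.

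### Device type is a declared stratum, but the t-test for objectives 1 and 2 has no device term and yields no device-specific reminder effect

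*SAP*

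**What the plan says.** Under the COVER PAGE heading, the SAP describes two versions of the reminder. Both devices send a text message. "Only the Flovent SmartInhaler featured an additional audio-visual reminder on the device". For that reason, "participants were stratified into two groups according to the type of SmartInhaler they were using". The recruitment target follows: "The aim was to recruit 15 participants to use the Flovent SmartInhaler and 15 participants to use the Qvar SmartInhaler". Device is not randomised: "Participants received either a Flovent or a Qvar SmartInhaler device depending on which daily controller medication they were taking".

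The visit 2 paragraph describes allocation to immediate or delayed activation: "participants were randomized by a block design to ensure participants were equally distributed among both study groups". It does not say whether the blocks ran within device.

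DATA ANALYSIS compares the mean adherence delta and the mean symptom-control delta "for each group using a student t-test". It names no device covariate, stratum or interaction and no estimate by device. The analysis of objective 3 does not separate the devices either.

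**The concern.** The plan names a factor that may change the effect of the intervention and stratifies on it. It then specifies a main analysis that does not mention it. Three things follow.

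- **Interpretation.** The reminder-on versus reminder-off difference averages a text-only reminder and a text-plus-alert reminder. No planned result shows whether the text alone works, which a team planning the larger trial would want to know.
- **Precision.** Any difference between devices in the deltas stays in the error term.
- **Balance.** If blocks ignored device, the arms can differ in device mix by chance, and the t-test cannot adjust for it.

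The word *group* is also used in two senses. The device strata are called two groups, and so are the randomised arms. DATA ANALYSIS does not say which it means.

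**Working it through.** **Inputs from the SAP.** 30 children, with a target of 15 per device; two randomised arms of equal size; power statement "with 15 patients in each group, with a power of 0.80, an alpha of 0.05" for a 15% change from 60% adherence.

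**Assumptions, because the SAP gives no figure.** SD of the delta 14 to 25 points; device gap 10 or 20 points; where effects are needed, 20 points (Flovent) and 10 points (Qvar).

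**1. The plan's own figure.** For a difference in means, the noncentrality is 15 / (SD × √(2/15)). With a two-sided t-test at 0.05, power reaches 0.80 only if the SD is about 14.2 points. Read as proportions, 60% versus 75% with 15 per arm has 13.6% power. With no SD stated, the 0.80 cannot be confirmed. That is a separate matter; an SD near 14 is used below because the stated power holds there.

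**2. Cost of a device term when device does not matter.** At SD 14, power is 80.8% for the t-test (28 df) and 80.7% with a device term (27 df).

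**3. Precision lost if the device gap d exists only in the activated arm.** With blocks within device, each arm holds 7 and 8 children per device, so the activated arm's variance rises by d² × (7/15)(8/15) = d² × 56/225.

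| SD | d | SE without gap variance | SE ignoring device | Inflation |
|---|---|---|---|---|
| 14 | 10 | √(2×196/15) = 5.11 | √((196+24.9+196)/15) = 5.27 | 3% |
| 14 | 20 | 5.11 | 5.72 | 12% |
| 25 | 10 | 9.13 | 9.22 | 1% |
| 25 | 20 | 9.13 | 9.49 | 4% |

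An additive device term does not remove all of this. It fits d/2 in both arms, leaving (d/2)² × 56/225 in each, which is half of the excess in total. At SD 14 and d = 10 the SE is √((392 + 12.4)/15) = 5.19, or 5.21 allowing for 27 df and the 7:8 split.

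**4. Background change differing by 10 points between devices** (SD 14.2, stratified allocation, 6,000 simulated trials).

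| | t-test | Device-adjusted |
|---|---|---|
| Type I error | 4.0% | 5.0% |
| Power for 15 points | 76.0% | 79.5% |

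With allocation not stratified by device, type I error is 5.3% and 5.4%. Neither allocation shows meaningful inflation.

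**5. Chance imbalance if blocks ignored device.** The number of Flovent children in one arm of 15 is hypergeometric (30, 15, 15). A 9:6 or worse split has probability 0.466; 10:5 or worse has 0.143. With effects of 20 and 10, and the extra alert acting only in the activated arm:

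- 9:6 gives (9×20 + 6×10)/15 = 16.0, a shift of 1.0 point from 15.
- 10:5 gives (10×20 + 5×10)/15 = 16.7, a shift of 1.7 points.

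Both are small beside a standard error of 5 to 9 points.

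**6. What device-specific results can carry.** With 7 and 8 children per cell, the 95% half-width is 2.16 × SD × √(1/7 + 1/8): about 16 points at SD 14 and 28 at SD 25. Within-device power for 15 points is about 48% at SD 14 and 27% at SD 20.

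**The case against.** **Pooling is inferred.** DATA ANALYSIS does not define its groups and could mean the device strata. This stands as a limit on certainty. The arms are the more natural reading, because the visit 2 paragraph sets up a concurrent control. If the device strata were meant, a two-group t-test would compare devices rather than reminder with control. Only a within-device comparison of run-in with intervention would give a text-only result, and the text does not describe one. On either reading of a two-group test, no reminder effect by device or adjusted for device is specified.

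**Pooling is a legitimate estimand for a pilot.** Both devices send the text, and the SAP seeks only a general estimate. This stands too, so the pooled question can remain the main one. It does not explain why a declared stratum is left out of the analysis.

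**The numerical harm is small.** This is correct. The 12% inflation needs a 20-point device gap, larger than the 15-point change the design targets, at the lowest assumed SD.

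**A reader might infer that the headline effect swings by nearly 7 points with recruitment.** That needs the assumed effects of 20 and 10 and device mixes of 25:5 versus 5:25: (25×20 + 5×10)/30 = 18.3 against (5×20 + 25×10)/30 = 11.7. The SAP sets a 15:15 target, where the value is 15. At Flovent shares of 30% to 70% it runs from 13 to 17. Nothing in the document suggests the extreme mixes.

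**Conclusion.** The point holds as a mismatch between the declared stratification and the specified analysis. It should be corrected, but it does not invalidate the comparison. The main harm is to interpretation, since no planned result isolates the text-only reminder. The precision loss is modest: 1–3% in the standard error for a 10-point gap in the activated arm, of which an additive term recovers about half, or 3.5 percentage points of power for a 10-point difference in background change. Imbalance matters only if blocks ignored device, and then moves the estimate by about 1–2 points at 9:6 to 10:5 under the assumed effects. All sizes rest on assumed SDs and device gaps, because the SAP gives neither.

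Two further inferences are not supported. One is that only device-specific estimates should inform the larger trial: they rest on 7 to 8 children per cell, and the SAP does not say which devices that trial would use. The other is that a between-device difference would measure the value of the audio-visual alert: device follows the child's existing controller medication, so alert and drug cannot be separated.

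**What to change.** In DATA ANALYSIS:

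- Define the groups as early versus delayed activation.
- Replace the t-test with a linear model of each delta on arm, with device (Flovent or Qvar) as a stratum term. Report the device-stratified arm difference with its 95% confidence interval as the main result.
- Report the arm difference and 95% confidence interval for each device, labelled descriptive because of the 7 to 8 children per cell.
- State that any between-device contrast is confounded with the controller drug.

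In the visit 2 paragraph, state whether the blocks were formed within device.

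The SAP is written in the past tense. If the t-test has already been run, keep it in the report beside the device-stratified result and date the change.

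The cost is a few sentences and lines of code, plus one degree of freedom (80.8% to 80.7% power at SD 14). Device is already known for every child. The device-specific intervals will be wide, with a standard error about 1.4 times the pooled one (14 × √(1/7 + 1/8) = 7.24 against 5.11 at SD 14).
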